8.2.4 Serious Adverse Event

An AE or SAR is considered “serious” if, in the view of either the investigator or DAIT/NIAID it results in any of the following outcomes (21 CFR 312.32(a)):

- Death: A death that occurs during the study or that comes to the attention of the investigator during the protocol-defined follow-up period must be reported whether it is considered treatment related or not.
- A life-threatening event: An AE or SAR is considered “life-threatening” if, in the view of either the investigator or DAIT/NIAID, its occurrence places the subject at immediate risk of death. It does not include an AE or SAR that, had it occurred in a more severe form, might have caused death.
- Inpatient hospitalization or prolongation of existing hospitalization.
- Persistent or significant incapacity or substantial disruption of the ability to conduct normal life functions.
- An event that requires intervention to prevent permanent impairment or damage. An important medical event that may not result in death, be life threatening, or require hospitalization may be considered an SAE when, based on appropriate medical judgment, it may jeopardize the participant and may require medical or surgical intervention to prevent one of the outcomes listed above.
- Congenital anomaly or birth defect.

8.2.5 “Expected” versus Unexpected Suspected Adverse Reaction

A suspected adverse reaction (SAR) is considered “expected” when it is listed in the General Investigational Plan of the IND or the protocol. A suspected adverse reaction is considered “unexpected” when the specificity or severity is not consistent with the risk information described in

the safety section provided in the General Investigational Plan of the IND or the protocol (21 CFR 312.32(a)). A suspected unexpected serious adverse reaction is referred to as a SUSAR.

8.3 COLLECTING AND RECORDING ADVERSE EVENTS

8.3.1 Methods of Collection

Adverse events, as defined by this protocol, will be collected from the time the participant signs the informed consent until the time an event is resolved or until 30 days after the participant completes study treatment, whichever comes first.

Adverse events may be collected as follows:

- Observing the participant.
- Questioning the participant in an objective manner.
- Receiving an unsolicited complaint from the participant.

An AE that is an asymptomatic abnormal value or result from a clinical or laboratory evaluation (e.g., a radiograph, an ultrasound, or an electrocardiogram) will be documented and maintained in the source records. Asymptomatic adverse events must be recorded on the AE CRF when they meet the criteria for a Grade 3 or greater AE per CTCAE criteria. The evaluation that produced the value or result should be repeated until that value or result returns to normal or can be explained and the participant's safety is not at risk.

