2.2 SECONDARY OBJECTIVES

1. To determine whether 134 weeks of peanut OIT induces tolerance in children with peanut allergy.
2. To assess the safety of peanut OIT and subsequent withdrawal of OIT in this population.
3. To define the immunological responses underlying desensitization and tolerance to peanut.

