3.3.2 Secondary Endpoints

Efficacy:

1. Tolerance Endpoint
The proportion of participants who pass both the blinded OFC to 10 g peanut flour (5 g peanut protein) and the Open OFC to 8 g peanut protein in natural food form at week 160.
Passing a blinded OFC is defined in [Section 3.3.1](#).
Passing an Open OFC is defined in Section 6.4.3.
2. Transient Desensitization Endpoint
This is the change in proportion of participants who pass the blinded OFC to 10 g peanut flour (5 g peanut protein) at week 134 and week 160.
Passing a blinded OFC is defined in [Section 3.3.1](#).
3. Highest Tolerated Cumulative Dose Endpoint
The highest tolerated cumulative dose of peanut protein during the blinded OFCs will also be collected and analyzed.

Safety:

1. The incidence of all adverse events.
2. Rates of withdrawal from OIT or placebo.

Mechanistic:

Changes in the following markers of immune mediation:

1. Secreted cytokines
2. Anti-peanut IgE, IgG, IgG4 and secretory IgA
3. Epitope arrays
4. IgE-facilitated, CD23-dependent allergen binding to B cells
5. Serum, stools, and saliva assays
6. PBMC expression of transcription factors and cytokines relevant to food allergy

7. CD4+ CD25+ FoxP3+ Tregs
8. DNA-HLA genotyping
9. Peanut-specific T cells
10. Ara h 1 and Ara h 2 reactive T cells
11. Th2A Subset Analysis Basophil activation
12. B cells

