8.2 DEFINITIONS

8.2.1 Adverse Event

An AE is any occurrence or worsening of an undesirable or unintended sign, symptom, laboratory finding, or disease that occurs during participation in the trial. An AE will be followed until it resolves or until 30 days after a participant terminates from the study, whichever comes first. All AEs

will be reported as specified in Sections [8.3](#) and [8.5](#) whether they are or are not related to disease progression or study participation.

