8.2.2 Study Specific Adverse Events

During the study it is anticipated that participants undergoing study procedures involving administration of peanut flour (blinded OFC, IDE, home or clinic OIT/placebo dosing) will experience allergic symptoms related to peanut allergy. Events related to these study procedures will be captured on procedure-specific forms, and will NOT be recorded as adverse events, unless they meet certain criteria as defined in [Section 8.3.2.2](#).

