8.3.2 Methods of Recording

8.3.2.1 Adverse Events

Throughout the study, the investigator will record all AEs, as defined by the protocol, on the appropriate CRF regardless of their severity or relation to study participation. The investigator will treat participants experiencing AEs appropriately and observe them at suitable intervals until their symptoms resolve or their status stabilizes.

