8.4 GRADING AND ATTRIBUTION OF ADVERSE EVENTS

8.4.1 Grading Criteria

8.4.1.1 Adverse Events Related to Study Procedures

Symptoms associated with systemic allergic reactions and/or anaphylaxis that occur during administration of peanut flour or placebo will be graded according to Table 3 below.

All AEs will be collected and recorded in the source documents from visit -1 until the time the participant completes the study (visit 27), or prematurely withdraws from the study. Table 3 was adapted from the grading of allergic reactions in the Consortium of Food Allergy Research (CoFAR3) protocol, entitled “Oral Desensitization to Egg with Subsequent Induction of Tolerance for Egg-Allergic Children”. CoFAR3 protocol is conducted under the IND #13239 sponsored by the DAIT/NIAID. This completed study assessed the oral desensitization to egg and induction of tolerance in egg-allergic children between the ages of 5 and 18 years (ClinicalTrials.gov Identifier: NCT00461097).

Table 3 Grading of Symptoms and Events Related to Peanut Flour Administration

Grade	1 (Mild)	2 (Moderate)	3 (Severe)	4 (Life threatening)
General	Transient or mild discomforts (< 48 hours)	Symptoms that produce mild to moderate limitation in activity some assistance may be needed	Marked limitation in activity, some assistance usually required Medical intervention; hospitalization is possible	Extreme limitation in activity, significant assistance required; Intervention is required; hospitalization is probable

Cardio-vascular			Hypotension Change in mental status	Persistent hypotension and/or hypoxia with resultant decreased level of consciousness associated with collapse and/or incontinence or other life threatening symptoms.
Skin	Skin flushing or pruritus, limited localized hives, swelling or rash	Persistent systemic hives, swelling		
Respiratory	Transient symptoms such as rhinorrhea, sneezing, nasal congestion, throat discomfort, and occasional cough	Wheezing without dyspnea, persistent cough	Bronchospasm, wheezing with dyspnea Laryngeal edema Throat tightness with hoarseness	
Gastro-intestinal	Abdominal discomfort, minor episode of vomiting	Persistent moderate abdominal pain, cramping, nausea Increased vomiting or other symptoms such as throat tightness without vomiting	Significant abdominal pain, cramping Repetitive vomiting	

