Adverse events related to study procedures other than peanut flour / placebo administration, will be graded according to the criteria set forth in the National Cancer Institute, *Common Terminology Criteria for Adverse Events, Version 4.03* (June 14, 2010) and documented on an Adverse Event form.

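### Section 8.3.1 ties the end of adverse event collection to the end of study treatment; the rest of the protocol collects adverse events to the end of study participation

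*Combined protocol and SAP*

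**What the plan says.** Section 8.3.1 (Methods of Collection) starts AE collection at informed consent and runs it "until the time an event is resolved or until 30 days after the participant completes study treatment, whichever comes first". Four other places bear on the same window:

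- Section 8.2.1 defines an AE as something that happens while the participant is in the trial. It follows an open AE to resolution or "until 30 days after a participant terminates from the study, whichever comes first".
- Section 8.3.2.1: "Throughout the study, the investigator will record all AEs, as defined by the protocol, on the appropriate CRF". It names no week or visit.
- Section 8.4.1.1 collects all AEs "from visit -1 until the time the participant completes the study (visit 27"), or until premature withdrawal.
- Appendix 2 marks AE assessment at every visit from 16 to 26, which includes weeks 136 and 160. In the text available, the visit-27 cell is blank.

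On treatment itself, section 3.1 describes 134 weeks of OIT or placebo and then 26 weeks of avoidance. Section 6.7.5 stops daily dosing after the week-134 challenge, and Table 1 shows a dose of zero from day 938.

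Secondary objective 2 (section 2.2) is "To assess the safety of peanut OIT and subsequent withdrawal of OIT in this population". The first safety endpoint (section 3.3.2) is "The incidence of all adverse events".

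**The concern.** The section that a site or data manager would consult for the collection window anchors it to the end of treatment. In this trial, treatment ends about six months before participation does. If that anchor were applied, non-serious AEs would be collected for only the first 30 days off treatment. Most of avoidance, and the week-160 visit with its challenges, would fall outside. Avoidance is the only period that can inform the withdrawal half of secondary objective 2, and the AE endpoint is stated without a time limit. If some sites used 8.3.1 and others used Appendix 2, AE incidence during avoidance would be hard to interpret.

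**Working it through.** **Inputs.** Build-up 30 weeks, maintenance 104, avoidance 26, post-challenge 2 (section 3.1). Days 938, 952, 1120 and 1134 are the nominal days of weeks 134, 136, 160 and 162 (Appendix 2). The 30-day limits are in 8.3.1 and 8.2.1. The visit windows are in section 6.1.1.

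**The plan's own calendar.** 30 + 104 = 134 weeks, and 134 × 7 = 938. 136 × 7 = 952, 160 × 7 = 1120 and 162 × 7 = 1134. All agree with the schedule.

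**Reading 1: 8.3.1 is a collection window.**

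- Close: 938 + 30 = day 968, and 968 / 7 = week 138.3.
- Avoidance: 1120 − 938 = 182 days. Outside the window: 1120 − 968 = 152 days, and 152 / 182 = 83.5%.
- For a participant who attends visit 27: 1134 − 968 = 166 of 1134 − 938 = 196 off-treatment days, or 84.7%.
- The week-136 visit (day 952) is inside the window. The week-160 visit (day 1120) is outside.

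**Do visit delays rescue it?** Visit 16 can fall as late as day 315, and later visits are timed from visit 16 with a window of −3 to +7 days.

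- Latest visit 24: 315 + 104 × 7 + 7 = day 1050. Close: 1050 + 30 = day 1080.
- Earliest visit 26 for the same participant: 315 + 130 × 7 − 3 = day 1222.

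The window still closes well before that participant's week-160 visit.

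**Reading 2: 8.3.1 only limits follow-up of open events.** It stops on day 968. Section 8.2.1 runs to 1120 + 30 = day 1150 for exit at week 160, or 1134 + 30 = day 1164 for exit at visit 27. That is 182 or 196 days later, so the conflict moves to 8.2.1.

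**What would and would not survive under reading 1.**

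- Serious AEs: still reported. Section 8.5.1 works from awareness of the event and sets no 30-day limit.
- Expected, related symptoms within two hours of the week-160 blinded challenge: still recorded on the dosing-specific form (8.3.2.2).
- Blinded-challenge events that are later than two hours, unexpected, or on the list of severe signs: 8.3.2.2 sends these to the AE record, which would already be closed.
- Open-challenge events: the exemption from AE recording in 8.2.2 covers procedures "involving administration of peanut flour (blinded OFC, IDE, home or clinic OIT/placebo dosing"). The open challenge uses peanut in natural food form. Section 8.4.1.1 sends events from other procedures to the AE form: "Adverse events related to study procedures other than peanut flour / placebo administration, will be graded". That route would be closed too.

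**The case against.** **The sentence is garbled and sets no clear rule.** A window for new events cannot close when one event resolves, so a follow-up limit was probably merged into the collection sentence. This stands as an account of how the text arose, and it rules out saying flatly that the protocol ends AE collection on day 968. It does not remove the problem, because the follow-up reading contradicts 8.2.1.

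**The week-160 challenge might count as study treatment.** Section 8.3.2.2 groups blinded challenges with product administration. On that reading the limit would be 1120 + 30 = day 1150, and the collection gap would vanish. The reading is not credible: sections 3.1 and 6.7.5 describe treatment as finished before avoidance begins.

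**Sites would follow the schedule anyway.** Appendix 2 marks AEs at weeks 136 and 160 and ongoing gastrointestinal symptoms at weeks 136, 160 and 162. The question in section 6.9.2 asks about change since the last visit, so it spans the avoidance interval. The safety analysis in 9.2.3.2 applies no 30-day cut-off. All of this stands, and it makes the harm conditional. It does not tell a site which section governs.

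**Stronger readings that a reader might infer.** One is that avoidance-phase AEs will be lost and withdrawal safety cannot be assessed. The documents do not support this, because most of the text directs collection through the whole study. Another is that the AE comparison between arms is biased. The 8.3.1 wording applies to both arms alike, and nothing in the documents shows a bias.

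**Conclusion.** Section 8.3.1 is internally inconsistent with the rest of the protocol and wrong as written. As a collection window it conflicts with 8.2.1 (the AE definition), 8.3.2.1, 8.4.1.1 and Appendix 2. As a follow-up limit it conflicts with the study-termination anchor in 8.2.1. This is an error of wording, not a questionable design choice.

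If 8.3.1 were followed, about 152 of 182 avoidance days (84%) would fall outside collection of non-serious AEs. That figure assumes the nominal schedule and full completion of treatment. With maximum visit delays the cut-off moves to day 1080, and the conclusion is unchanged. The consequence is confined to safety data: the withdrawal part of secondary objective 2 and the all-AE endpoint. Serious AEs and early, expected blinded-challenge symptoms are protected. Open-challenge events, and blinded-challenge events that are late, unexpected or on the severe list, are not. No efficacy analysis is touched.

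Two smaller mismatches belong with this one. Collection starts at consent in 8.3.1 but at visit -1 in 8.4.1.1, while Appendix 1 already marks AEs at visit -2. Little turns on this, since section 6.7.1.2 lets visits -2 and -1 share a day. Section 8.4.1.1 names visit 27 as the end, but the Appendix 2 AE cell for that visit reads as blank.

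**What to change.** - Reword 8.3.1 so that AEs are collected from informed consent through each participant's last study visit: week 160, visit 27 where it applies, or premature withdrawal.
- Keep the 30-day limit only in 8.2.1, anchored to study termination, as the rule for following events still open.
- Change the start in 8.4.1.1 to informed consent.
- Check the visit-27 AE cell in Appendix 2 against the source table, and reconcile it with 8.4.1.1.

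The cost is wording in two sections and at most one mark in a table. Weeks 136 and 160 and visit 27 are already scheduled, so no visit is added. Under section 9.4, a change to a principal feature of the design or analysis plan needs an amendment. Even if this correction falls outside that rule, it should go to all sites in writing so that they apply one window.

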8.3.2 Methods of Recording

8.3.2.1 Adverse Events

Throughout the study, the investigator will record all AEs, as defined by the protocol, on the appropriate CRF regardless of their severity or relation to study participation. The investigator will treat participants experiencing AEs appropriately and observe them at suitable intervals until their symptoms resolve or their status stabilizes.

8.3.2.2 Adverse Events Occurring During Peanut Flour / Placebo Administration

Guidelines for recording events that occur during investigational product or placebo administration, which include blinded OFC, IDE and daily home and clinic dosing:

All symptoms or events that occur within two hours and that are expected according to the General Investigational Plan and related to administration of investigational product or placebo will be recorded on the dosing-specific CRFs for blinded OFC, IDE, home or clinic dosing. They will be graded according to table 3 ([Section 8.4](#)).

Any of the following symptoms or events that occur at any time related to dosing, should also be recorded as an adverse event:

- hypotension
- cyanosis
- SpO₂ < 92%
- confusion
- collapse
- loss of consciousness

- incontinence
- required more than 2 injections of epinephrine

Any such symptom or event that meets the serious criteria in [Section 8.2.4](#) will also be reported as an SAE.

Any symptom or event that occurs more than two hours after dosing will be recorded as an adverse event.

Any symptom or event that is not expected according to the General Investigational Plan will be recorded as an adverse event.

8.3.2.3 Serious Adverse Events Related to Peanut Flour / Placebo Administration

If systemic allergic reactions, anaphylaxis, and Eosinophilic Esophagitis meet the criteria for Serious Adverse Event, as defined in [Section 8.2.4](#), they will be recorded on the SAE CRF within 24 hours and the FDA will be notified as outlined in [Section 8.5](#).

An SAE notification will be sent by Rho Safety within 24 hours to the DAIT/NIAID Medical Monitor, the Protocol Chair or co-Chair, and the ITN Clinical Trial Physician. Together the DAIT/NIAID Medical Monitor, the Protocol Chair or co-Chair, and the ITN Clinical Trial Physician will determine whether the SAE meets expedited reporting criteria and if stopping rules ([Section 3.4.1](#)) have been met.

8.4 GRADING AND ATTRIBUTION OF ADVERSE EVENTS

8.4.1 Grading Criteria

8.4.1.1 Adverse Events Related to Study Procedures

Symptoms associated with systemic allergic reactions and/or anaphylaxis that occur during administration of peanut flour or placebo will be graded according to Table 3 below.

All AEs will be collected and recorded in the source documents from visit -1 until the time the participant completes the study (visit 27), or prematurely withdraws from the study. Table 3 was adapted from the grading of allergic reactions in the Consortium of Food Allergy Research (CoFAR3) protocol, entitled “Oral Desensitization to Egg with Subsequent Induction of Tolerance for Egg-Allergic Children”. CoFAR3 protocol is conducted under the IND #13239 sponsored by the DAIT/NIAID. This completed study assessed the oral desensitization to egg and induction of tolerance in egg-allergic children between the ages of 5 and 18 years (ClinicalTrials.gov Identifier: NCT00461097).

Table 3 Grading of Symptoms and Events Related to Peanut Flour Administration

Grade	1 (Mild)	2 (Moderate)	3 (Severe)	4 (Life threatening)
General	Transient or mild discomforts (< 48 hours)	Symptoms that produce mild to moderate limitation in activity some assistance may be needed	Marked limitation in activity, some assistance usually required Medical intervention; hospitalization is possible	Extreme limitation in activity, significant assistance required; Intervention is required; hospitalization is probable

Cardio-vascular			Hypotension Change in mental status	Persistent hypotension and/or hypoxia with resultant decreased level of consciousness associated with collapse and/or incontinence or other life threatening symptoms.
Skin	Skin flushing or pruritus, limited localized hives, swelling or rash	Persistent systemic hives, swelling		
Respiratory	Transient symptoms such as rhinorrhea, sneezing, nasal congestion, throat discomfort, and occasional cough	Wheezing without dyspnea, persistent cough	Bronchospasm, wheezing with dyspnea Laryngeal edema Throat tightness with hoarseness	
Gastro-intestinal	Abdominal discomfort, minor episode of vomiting	Persistent moderate abdominal pain, cramping, nausea Increased vomiting or other symptoms such as throat tightness without vomiting	Significant abdominal pain, cramping Repetitive vomiting	

Adverse events related to study procedures other than peanut flour / placebo administration, will be graded according to the criteria set forth in the National Cancer Institute, *Common Terminology Criteria for Adverse Events, Version 4.03* (June 14, 2010) and documented on an Adverse Event form.

8.4.1.2 All Other Adverse Events

Adverse events not associated with study procedures will be graded according to the criteria set forth in the NCI-CTCAE National Cancer Institute's *Common Terminology Criteria for Adverse Events* (v 4.03) manual which provides a common language to describe levels of severity, to analyze and interpret data, and to articulate the clinical significance of all AEs.

Adverse events will be graded on a scale from 1 to 5 according to the following standards in the NCI-CTCAE manual:

- Grade 1 = mild adverse event
- Grade 2 = moderate adverse event
- Grade 3 = severe and undesirable adverse event
- Grade 4 = life-threatening or disabling adverse event
- Grade 5 = death

For additional information and a printable version of the NCI-CTCAE manual, go to <http://ctep.cancer.gov/reporting/ctc.html>

8.4.2 Attribution Definitions

The site investigator will make the initial determination of the relation, or attribution, of an AE to study drug and will record the initial determination on the appropriate CRF and/or SAE reporting form. The relation of an AE to study drug will be determined using definitions in Table 4. Final determination of attribution for safety reporting will be decided by DAIT, NIAID.

Table 4 Attribution of Adverse Events

Code	Descriptor	Definition
Unrelated Category		
1	Unrelated	The adverse event is clearly not related.
Related Categories		
2	Possible	The adverse event has a reasonable possibility to be related; there is evidence to suggest a causal relationship.
3	Probable	The adverse event is likely related.
4	Definite	The adverse event is clearly related.

8.5 REPORTING SERIOUS ADVERSE EVENTS

8.5.1 Reporting SAEs to the IND Sponsor

The following process for reporting an SAE ensures compliance with 21CFR 312 and ICH guidelines. After learning that a participant has experienced an SAE, the investigator or designee will report the SAE to the DAIT/NIAID, the IND sponsor for this protocol, via the electronic SAE report form (SAE CRF) within 24 hours of becoming aware of the event. The initial SAE CRF should include as much information as possible, but at a minimum must include the following:

- AE term
- Study drug treatment
- Relationship to study medications
- Reason why the event is serious
- Supplementary CRF pages that must be current at the time of SAE reporting: medical history, concomitant medications, demographics, study drug administration, death.

As additional details become available, the SAE CRF should be updated and submitted. Every time the SAE CRF is submitted, it should be electronically signed by the investigator or sub investigator.

For additional information regarding SAE reporting, contact Rho Product Safety:

Rho Product Safety
[name]
[name]
Toll-free [contact]
SAE Fax Line: [name]
Email: [contact]

